**8.2 Dose Modifications**

NOTE: PRO-CTCAE data should not be used for determining dose delays or dose modifications or any other protocol directed action.

- a. Dose interruption or delay is permitted for toxicity or administrative reasons. If toxicity is deemed attributable to any single agent, then dose delay or missed dose of any single agent is allowable (ie, nivolumab, BV, A, V, or D alone may be delayed or missed or the entire regimen (N-AVD or B-AVD) may be delayed or missed at the discretion of the treating investigator.
  1. If all drugs are held  $> 3$  and  $\leq 28$  days after the protocol-scheduled date, the total treatment is considered delayed.
    - a. The next treatment after a delayed dose should occur as soon as possible (per the treatment schedule) once all toxicities resolve per the adverse event tables below or once the administrative delay is addressed.
    - b. The reason for delay must be documented.
    - c. When treatment is resumed, the treatment should be counted as the treatment cycle that was originally due at the earlier protocol-scheduled date, and the calendar will reset for subsequent visits.
      - For example, if C2/D15 dose is delayed by 10 days and is administered on D25 of Cycle 2, then the calendar will reset on Day 25 and the next scheduled dose will be scheduled to be administered 14 days later on what would have originally been Cycle 3/Day 11 (and will be counted as C3/D1).

2. If an individual drug is held for >3 days, then respective dose of the individual drug (e.g. vinblastine) will be considered a missed dose, and when the individual drug is resumed (once all toxicities have improved per the adverse event tables), it will be counted as the next scheduled dose.
  - a. Missed doses may not be made up.
  - b. Data submission for the missed dose will reflect the reason for missed dose.
3. A total treatment interruption [i.e. stopping all study drugs nivolumab and AVD or BV and AVD] of > 28 days will require the patient to go off-protocol therapy].

b. Hematologic Toxicity:

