Although it has been common practice in adult oncology settings in the United States to attenuate doses or delay treatment due to cytopenias alone, recent studies have shown that this policy is unnecessary and inadvisable for patients receiving ABVD and results in suboptimal treatment outcomes. (97,98) Patients should receive full doses of AVD on schedule on Days 1 and 15 of each 28 day cycle without treatment delays, unless neutropenic fever or documented infections are present. In nearly all cases, counts will recover despite administration of the next course of full dose chemotherapy administered on time. (99, 100)

c. Arm 1: N-AVD

The following tables summarize the criteria for nivolumab dose delays. The dose of nivolumab should not be modified. If dose delay criteria are met, the entire dose of nivolumab is held until the patient meets criteria for nivolumab re-initiation and then the patient should resume full dose nivolumab. In the event of a nivolumab-related AE that requires hold or discontinuation of nivolumab, AVD may be continued (dose reductions may be necessary according to [Section 8.2](#) above). If nivolumab is withheld for > 6 weeks due to nivolumab-related toxicity, nivolumab should be permanently discontinued.

If patient is unable to receive *ALL components* of study therapy (i.e: Nivolumab as well as A, V, and D) > 4 weeks (for any reason), then patient must go off protocol treatment.

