## 1. Dose Modification and Management for Myocarditis

- Nivolumab will be held for Grade 2 cardiac dysfunction pending evaluation.
- Nivolumab will be permanently discontinued for Grade 3 or 4 cardiac dysfunction and Grade 2 events that do not recover to normal parameters or that reoccur.
- Treatment with steroids as clinically indicated.
- For cardiomyopathy without evidence of myocarditis, please call the Study Chair to determine management (e.g. doxorubicin dose modification).

Cardiac a, c	Management/Next Dose for BMS-936558 (Nivolumab) Cardiac Toxicities
Grade 1	Hold nivolumab pending evaluation and observation. b Evaluate for signs and symptoms of CHF, ischemia, arrhythmia or myositis. Obtain history EKG, CK (for concomitant myositis), CK-MB. Repeat troponin, CK and EKG 2-3 days. If troponin and labs normalize may resume therapy. If labs worsen or symptoms develop then treat as below.
Grade $\geq 2$ with suspected myocarditis	Hold nivolumab. b Admit to hospital. Cardiology consult. Rule out MI or other causes of cardiac disease. Cardiac Monitoring. Cardiac Echo. Consider cardiac MRI and cardiac biopsy. Initiate high dose methylprednisolone. If no improvement within 24 hours, add either infliximab, antithymocyte globulin (ATG) or tacrolimus. Resume therapy if there is a return to baseline and myocarditis is excluded or considered unlikely.
Grade $\geq 2$ with confirmed myocarditis	Discontinue nivolumab. Admit to CCU (consider transfer to nearest Cardiac Transplant Unit, if appropriate). Treat as above. Consider high dose methylprednisolone. Add ATG or tacrolimus if no improvement. Off protocol treatment.
a	Including CHF, LV systolic dysfunction, Myocarditis, CPK, and troponin.
b	Patients with evidence of myositis without myocarditis may be treated according as "other event". See "All other treatment-related events" in Section 8.2c.2 .
c	Pericarditis events should be managed according to the "Other treatment-related adverse events" category at the end of the table in Section 8.2c.2 .
Note: The optimal treatment regimen for immune mediated myocarditis has not been established. Since this toxicity has caused patient deaths, an aggressive approach is recommended.	

2. Dose Modification and Management for all other Adverse Events

Treatment-related Adverse Event	Grade of Event	Management for Nivolumab
Nephritis	≤ Grade 1	No change.

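### Section 8.2c.1 gives conflicting nivolumab instructions for a recovered Grade 3–4 cardiac event in which myocarditis was suspected and then ruled out or judged unlikely

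*Combined protocol and SAP*

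**What the plan says.** Section 8.2c.1 of the combined protocol and SAP covers nivolumab management for cardiac toxicity in Arm 1, first in bullets and then in a table.

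- **Bullets.** Grade 2 cardiac dysfunction means a hold while it is evaluated. At the next level, "Nivolumab will be permanently discontinued for Grade 3 or 4 cardiac dysfunction"; the same bullet also stops the drug for Grade 2 events that fail to recover or that come back. A later bullet reads "For cardiomyopathy without evidence of myocarditis, please call the Study Chair to determine management", with doxorubicin modification as its example.
- **Table.** The column is headed as nivolumab management. Footnote a brings in heart failure and left ventricular systolic dysfunction. The suspected-myocarditis row starts at Grade 2 and has no ceiling. It requires a hold, admission and a cardiology consult, tells the site "Rule out MI or other causes of cardiac disease", and ends "Resume therapy if there is a return to baseline and myocarditis is excluded or considered unlikely". Only the confirmed-myocarditis row stops nivolumab for good.
- **Lead-in, Section 8.2c.** "The following tables summarize the criteria for nivolumab dose delays". Nivolumab is "held until the patient meets criteria for nivolumab re-initiation and then the patient should resume full dose nivolumab".

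**The concern.** Two safety rules in one subsection, for the same drug, reach the same patients and disagree. A site that reads the bullet stops nivolumab permanently; a site that reads the row restarts it at full dose. Each can say that it followed the protocol.

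Either error has a cost. If the bullet is what was intended, the row permits rechallenge after a severe cardiac event, including when myocarditis has not been excluded but is only thought unlikely. If the row is what was intended, the bullet takes the experimental drug away from a patient whose event may have had an unrelated cause such as myocardial infarction. The situation can be foreseen: all Arm 1 patients also receive doxorubicin, Section 3.3 lists cardiomyopathy among its boxed warnings, and Section 7.3 plans for heart failure, infarction or cardiomyopathy arising after treatment starts.

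**Working it through.** The plan states no figure to reproduce. The check is a comparison of the two rules, case by case.

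| Event | Bullets | Table | Same answer? |
|---|---|---|---|
| Grade 2, first event, suspected, recovers, myocarditis ruled out or unlikely | Hold, no permanent stop | Hold, then resume | Yes |
| Grade 2, suspected, does not recover | Permanent stop | Condition for resuming not met | Yes in effect |
| Grade 3–4, myocarditis confirmed | Permanent stop | Permanent stop | Yes |
| Grade 3–4, suspected, does not recover | Permanent stop | Condition for resuming not met | Yes in effect |
| Grade 3–4, suspected, recovers, myocarditis ruled out or unlikely | Permanent stop | Resume | **No** |

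Several readings might remove the conflict in the last line.

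1. *Resumption refers to AVD only.* The column is nivolumab-specific and the row opens by holding nivolumab, so this does not work.
2. *The recovery and recurrence wording in the bullet also qualifies Grade 3–4.* Then Grades 2, 3 and 4 would share one rule, and there would be no reason to list Grade 2 separately.
3. *The table prevails.* The Section 8.2c lead-in supports treating the table as the operative rule. It does not exempt these events from a permanent stop written in the same subsection.
4. *The Study Chair bullet settles it.* It covers cardiomyopathy without evidence of myocarditis. It does not reach the other causes that the row tells sites to look for, and it does not say which nivolumab rule governs.
5. *Footnotes b and c.* They redirect myositis and pericarditis only.
6. *The six-week limit in Section 8.2c.* It makes a hold for nivolumab-related toxicity permanent after six weeks. It does not decide an event that recovers sooner or is attributed to something else.

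Size for one patient, from the schedule in Sections 7.1a and 7.3a:

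- Planned nivolumab doses = 2 per cycle × 6 cycles = 12.
- After an event following dose k, the bullet allows 0 further doses and the row allows at most 12 − k.
- k = 1: 0 against up to 11. k = 4: 0 against up to 8. k = 8: 0 against up to 4. k = 11: 0 against up to 1.

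The values of k are illustrative. The row's figure is an upper limit, because Section 8.2a.2 says of an individual drug held back that "Missed doses may not be made up".

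**The case against.** The best reply accepts that the texts differ and says that the practical risk is already contained.

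- **A decision-maker is available for any cause.** Section 7.0 and the contact page give a study-chair line for dose-modification, treatment and toxicity questions, infarction included. The table of contents also lists a Section 8.3 on dose-modification contacts, which is not in the text available for this review.
- **The study chairs will see these events.** The row requires admission. Under Table 8.1 a serious Grade 3 event needs a report within 10 calendar days, and a Grade 4 event needs 24-hour notice and a full report within 5 further days. Section 11.3 has the study chairs review serious events on notification.
- **Resumption is guarded.** Section 7.3 and footnote g of Section 9.1 recommend cardiology review and cardiac testing before each cycle, as clinically indicated. Section 7.8 allows removal for unacceptable toxicity.

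All of this stands, and it makes undetected divergence between sites unlikely. It does not remove the conflict. A site that reads only one of the two rules sees nothing to ask about, and no route states which rule the study chair should apply.

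Two stronger readings are tempting and are not supported. A reader might take "Since this toxicity has caused patient deaths, an aggressive approach is recommended" as evidence that the row exposes patients to a fatal risk. That note concerns immune-mediated myocarditis itself; the disputed patients have recovered and had it ruled out or judged unlikely, so the note bears only on a residual misdiagnosis among those judged unlikely. A reader might also infer that the bullet must be the correct rule because it is stricter. The documents do not say so: which rule is right is a clinical choice, and an absolute Grade 3–4 stop would sit awkwardly with the Study Chair bullet, which has no grade limit.

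**Conclusion.** The conflict is real and the text is wrong as written, within narrow bounds. It applies to Arm 1 patients with an event that a site would grade as Grade 3–4 cardiac dysfunction, such as heart failure or left ventricular systolic dysfunction, with myocarditis suspected, return to baseline, and myocarditis then ruled out or judged unlikely. The bullet does not define cardiac dysfunction, so an isolated CPK or troponin rise is not included.

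The subset is small and cannot be counted from the documents. A reader might infer a number from the nivolumab risk list in Section 3.1c, which places myocarditis and cardiomyopathy below 3%: 0.03 × 470 Arm 1 patients = 14.1. That is neither an estimate nor a bound, because events suspected and then ruled out are a different group.

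Nor do the documents support a claim of harm to the trial's inference. Section 11.2 analyzes eligible patients as randomized whatever treatment they received, and alpha, power and sample size do not depend on this rule. The issue is dosing safety and consistency between sites. It should be fixed because two explicit instructions oppose each other and reconciling them costs almost nothing.

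**What to change.** Make the bullet and the row agree, in one of two ways.

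1. **Keep the strict rule.** Limit the row's permission to resume to Grade 2, so that Grade 3–4 stays a permanent stop, and state how that stop applies to patients sent to the Study Chair under the cardiomyopathy bullet.
2. **Allow rechallenge.** Add to the bullet an exception for Grade 3–4 events, only after return to baseline, with myocarditis excluded and with Study Chair approval. Section 8.2c.2 already uses that approval step for a Grade 3 infusion reaction. The row should then point to the exception for Grade 3–4, because its present condition is looser.

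The study chairs and the IND holder should choose. Until they do, sites should follow the stricter course: no nivolumab rechallenge after a Grade 3–4 event without Study Chair approval.

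The cost is a one-sentence wording correction in one section, plus the pointer under option 2. No data collection or analysis changes.

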4. Cautionary concomitant medications:
  - The use of strong inhibitors or inducers of CYP1A2 (dacarbazine interaction) or CYP3A4 (doxorubicin, brentuximab vedotin, vinblastine interactions) should be avoided. See [Section 18.9](#).
  - Multiple CYP3A4 interacting agents of moderate or strong effect in the HIV+ patients should not be used. This includes most HIV protease inhibitors.

c. **Supportive Care Guidelines**

1. **Infusion-related reactions:**

All infusions should be administered at a site properly equipped and staffed for anaphylaxis should it occur.

Medications for treatment of hypersensitivity reactions, such as epinephrine, antihistamines, and steroids, should be available for immediate use in the event of a reaction during administration.

See [Section 8.2c.2](#) for dose modification guidelines.

2. **Nausea and/or vomiting:**

Although the study does not require prophylactic antiemetics, there is no prohibition against their use. Treating investigators should follow institutional guidelines for administration of antiemetics.

3. **Suspected Progressive Multifocal Leukoencephalopathy (PML):**

Signs and symptoms of PML may include altered mental status; motor deficits, such as hemiparesis or ataxia; visual disturbances; or higher cortical dysfunction, such as dysphasia or agnosia. Seizures have also been reported in patients with PML (approximately 20%). The onset of neurological deficits may occur over weeks to months.

See [Section 8.2b](#) for dose modification guidelines.

4. Suspected immune reaction to nivolumab:

See [Section 8.2c.2](#) for dose modification guidelines and [Section 18.3](#) for detailed algorithms for Immuno-Oncology management of the following groups of AEs:

- Gastrointestinal
- Renal
- Pulmonary
- Hepatic
- Endocrinopathies
- Skin
- Neurological

5. Antimicrobial prophylaxis

Pneumocystis pneumonia (PCP) is known to occur in patients with compromised immune systems and has been reported in patients receiving ABVD-based therapy, including BV+AVD. PCP prophylaxis should be considered at the discretion of the treating investigator for both arms, particularly in patients treated on Arm 2 (BV+AVD).

Antimicrobial prophylaxis (such as fluconazole, acyclovir, levofloxacin) is allowed at the discretion of the treating investigator and should be administered per standard of care and institutional procedures.

6. Additional monitoring recommended for patients with pericardial effusion at time of registration

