	Grade 4	Permanently discontinue nivolumab.
	See also: Section 18.3 for Skin Adverse Event Management Algorithm.	
Ocular toxicities (uveitis, iritis)	$\leq$ Grade 1	No change.
	Grade 2	
 
Consider holding nivolumab, treat with topical steroids such as 1% prednisolone acetate suspension.
 
Evaluation by ophthalmologist strongly recommended.
 

	Grade 3	
 
Hold nivolumab.
 
Treat with systemic corticosteroids such as 1-2mg/kg of prednisone.
 
Evaluation by ophthalmologist strongly recommended.
 

	Grade 4	
 
Permanently discontinue nivolumab.
 
Treat with systemic corticosteroids such as 1-2mg/kg of prednisone.
 

Abnormal liver function (AST/ALT, Total bilirubin, immune-related hepatitis)	$\leq$ Grade 1	No change.
	Grade 2	
 
Nivolumab management: hold nivolumab until <math><</math> Grade 2 or baseline.
 
AVD management: If the bilirubin rises to <math>> 2 \times</math> ULN (but <math>\leq 5 \times</math> ULN), the doxorubicin and vinblastine doses must be reduced by 50% of last dose received to avoid undue hepatic toxicity. Full doses should be given once the bilirubin is <math>\leq 2 \times</math> ULN.
 

	Grade 3	
 
AVD management: If the bilirubin rises to <math>\geq 5 \times</math> ULN, then hold doxorubicin and vinblastine.
 
Nivolumab management: hold nivolumab until <math><</math> Grade 2 or baseline. If AST/ALT<math>>8</math>x ULN or bilirubin <math>>5</math>x ULN, permanently discontinue nivolumab.
 

	Grade 4	Permanently discontinue nivolumab.

If patient has concurrent AST or ALT <math>> 3 \times</math> ULN and total bilirubin <math>> 2 \times</math> ULN, then permanently discontinue nivolumab.
 
See also Section 18.3 for Hepatic Adverse Event Management Algorithm.
		

Treatment-related Adverse Event	Grade of Event	Management for Nivolumab
Amylase or lipase, associated with GI symptoms	$\leq$ Grade 1	No change.
	Grade 2	No change.
	Grade 3	No change if asymptomatic. If GI symptoms, hold nivolumab until asymptomatic and $<$ Grade 3.

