## Hepatic Adverse Event Management Algorithm

Rule out non-inflammatory causes. If non-inflammatory cause, treat accordingly and continue I-O therapy. Consider imaging for obstruction.

Patients on IV steroids may be switched to an equivalent dose of oral corticosteroids (e.g. prednisone) at start of tapering or earlier, once sustained clinical improvement is observed. Lower bioavailability of oral corticosteroids should be taken into account when switching to the equivalent dose of oral corticosteroids.

\*I-O therapy may be delayed rather than discontinued if AST/ALT ≤ 8 x ULN and T.bili ≤ 5 x ULN.

[figure not shown]
\*\*The recommended starting dose for grade 4 hepatitis is 2 mg/kg/day methylprednisolone IV.

d. Neurological Adverse Event Management Algorithm

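### The hepatic footnote in 18.3c allows nivolumab to be delayed without repeating the combined AST/ALT and bilirubin rule that requires a permanent stop in 8.2c.2

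*Combined protocol and SAP*

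**What the plan says.** The abnormal liver function row of the Arm 1 table in 8.2c.2 holds nivolumab at Grade 2 and at Grade 3 until the event is below Grade 2 or back to baseline, and stops it for good at Grade 4. It has two further permanent-stop rules:

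- In the Grade 3 entry, AST/ALT above 8 times ULN or bilirubin above 5 times ULN leads to "x ULN, permanently discontinue nivolumab".
- In the note that closes the row, beginning "If patient has concurrent AST or ALT", a transaminase above 3 times ULN together with total bilirubin above 2 times ULN leads to "ULN, then permanently discontinue nivolumab". The note has no upper bound, grade limit or exception.

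The line directly after that note refers to the hepatic algorithm in 18.3. In 18.3c a footnote marked with a single asterisk reads "I-O therapy may be delayed rather than discontinued if AST/ALT ≤ 8 x ULN and T.bili ≤ 5 x ULN". A second footnote, with two asterisks, concerns the steroid starting dose in Grade 4 hepatitis.

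On the roles of the two sections, 7.2c.4 cites 8.2c.2 for dose modification and 18.3 "for detailed algorithms for Immuno-Oncology management of the following groups of AEs", with hepatic events among those groups. Section 8.2c introduces its own tables with "The following tables summarize the criteria for nivolumab dose delays".

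**The concern.** The footnote carries the 8-fold and 5-fold limits of the Grade 3 stop rule but not the combined-rise rule. It joins its two conditions with an and, so a patient with both tests moderately raised can meet it directly. It also speaks of delaying rather than discontinuing, and discontinuing is exactly what the closing note demands.

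The stake is patient safety. A site working from the footnote could hold nivolumab and later restart it in a patient whom 8.2c.2 says must not receive it again. The nivolumab risk list in 3.1 names hepatic failure among the immune-mediated disorders that may be severe and possibly fatal.

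**Working it through.** The protocol gives no figure to reproduce here, and no sample size, power or error rate is involved. The check sets the two rules side by side. Write T for the higher of AST and ALT and B for total bilirubin, both as multiples of ULN.

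- Closing note of the liver row, 8.2c.2: if T > 3 and B > 2, stop permanently.
- Footnote, 18.3c: if T ≤ 8 and B ≤ 5, delay may replace discontinuation.

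Taken literally, both conditions hold when 3 < T ≤ 8 and 2 < B ≤ 5. Two illustrative points inside that overlap and two outside it:

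| T | B | 8.2c.2 closing note | 18.3c footnote wording | Differ? |
|---|---|---|---|---|
| 4 | 2.5 | Stop permanently | Delay permitted | Yes |
| 7 | 4 | Stop permanently | Delay permitted | Yes |
| 9 | 2.5 | Stop permanently | No permission to delay | No |
| 7 | 1.8 | Does not apply | Delay permitted | No |

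In the third line the Grade 3 limit on AST/ALT also requires a stop. In the fourth, the closing note is silent, so the footnote permits nothing that the note forbids.

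Next, does any text settle the overlap? Section 7.2c.4 assigns dose modification to 8.2c.2, and 8.2c says its tables hold the nivolumab delay criteria. Both point towards 8.2c.2. Neither says what to do when 18.3 reads differently. The protocol does state precedence elsewhere: 15.1 tells sites to follow the protocol when the specimen website differs from it. That concerns an outside source rather than two protocol sections, but it shows the form such a sentence could take.

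Finally, what cannot be checked: the single-asterisk footnote qualifies a box in the 18.3c flow chart, and the chart is not available in the text reviewed. The table above therefore compares the footnote's wording with the note. It does not show at which grades the algorithm applies the footnote.

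**The case against.** The best counter-argument has four parts.

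1. The footnote is a fragment of a figure that cannot be seen. The asterisk may sit only on higher-grade boxes, and a box may itself carry the combined-rise exception. **This stands as a limit.** A reader might infer that the whole algorithm contradicts the table for every value with AST or ALT above 3 to 8 times ULN and bilirubin above 2 to 5 times ULN. The documents do not support that; only the footnote wording can be compared.

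2. The protocol already divides the roles, and holding or stopping nivolumab is a dose-modification question. **This largely stands**, and it makes a misreading less likely. It does not amount to a statement that 8.2c.2 prevails.

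3. The table is mandatory and specific, while the footnote is permissive and written for immuno-oncology therapy in general. The skin algorithm in the same appendix still cites CTCAE version 4 although 8.1 sets version 5.0, which suggests material carried over from a general template. A site that stops nivolumab satisfies both texts. **All true**, but the appendix still permits what the table forbids.

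4. A reader reaches 18.3 from the line immediately after the stop rule, so has just read it. **True for that route.** A reader who goes straight to the appendix, which is titled for Arm 1 adverse event management, has not.

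A reader might also infer that 8.2c.2 contradicts itself, because the row holds at Grades 2 and 3 while its closing note stops. It does not: the note reads naturally as an override for the whole row.

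**Conclusion.** The inconsistency is real at the level of wording. The 18.3c footnote allows delay at AST/ALT up to 8 times ULN and total bilirubin up to 5 times ULN, without the combined-rise exception that the 8.2c.2 closing note makes mandatory. The more natural reading is that 8.2c.2 decides, but the protocol leaves this to inference.

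The practical size is small. The situation should be uncommon, the documents give no basis for a count, and an error requires a site to rely on the footnote over the table. The two readings also converge if liver tests do not recover, because 8.2c adds "If nivolumab is withheld for > 6 weeks due to nivolumab-related toxicity, nivolumab should be permanently discontinued". A reader might try to express the harm as extra doses given. That would assume both the misreading and the recovery, and would say nothing about how often either occurs.

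There is no effect on power, type I error or sample size. The conclusion assumes that the footnote text is complete as read and that no unseen chart box supplies the exception.

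**What to change.** Either of two changes is enough:

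- Extend the 18.3c footnote with a clause such as: *except when AST or ALT > 3 x ULN and total bilirubin > 2 x ULN occur together, in which case permanently discontinue nivolumab per Section 8.2c.2*.
- State once, in 8.2c.2 or at the head of 18.3, that *Section 8.2c.2 governs nivolumab dosing where it differs from Section 18.3*.

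The sponsor holds the flow chart and can first see whether a box already carries the exception. If it does, the footnote should still be brought into line with it. The cost is one clause or one sentence at the next amendment, with no added tests, visits or patients.
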